8.1.2 Adverse Events of Special Interest

In addition, we will specifically evaluate infants for the following adverse events of special interest:

1. Bradycardia (need for pharmacologic intervention, or a persistent heart rate below 100 while awake and alert after drug administration) (per study clinician or per parent report if informed by another clinician)
2. Hypotension (need for pharmacologic intervention, or blood pressure < 80% standard values for age) (per study clinician or per parent report if informed by another clinician)
3. New alteration in mental status (e.g., drowsiness, lethargy) (per study clinician or parent report)
4. New local skin irritation (per study clinician or parent report)
5. New sleep disturbance (per study clinician or parent report)
6. Apnea (per study clinician or parent report)
7. Bronchospasm (evaluated by study clinician when clinically indicated or per parent report if informed by another clinician)
8. Hypoglycemia (serum glucose < 60 mg/dL) (evaluated by study clinician when clinically indicated or per parent report if informed by another clinician)
9. Diarrhea (per parent report)
10. Arrhythmias

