In contrast to the few documented AEs in the above studies, investigators documented episodic bradycardia in 4 of 22 infants who received Holter monitoring concomitant with timolol therapy for IH.²⁴ Two of these infants with clinically significant bradycardia had weights <2500 g at the initiation of therapy, both were <40 weeks postmenstrual age (PMA) at drug initiation, and both were receiving a timolol dose higher than most of the cohort.²⁴ In a case report of an infant treated with ophthalmic timolol and anti-glaucoma medications, the infant developed altered mental status, hypotonia, hypothermia, bradycardia, apnea, hypotension, and bronch- obstruction, and required intensive care.²⁵ A second case report documented apneic spells in a 2-week-old premature infant who was receiving timolol therapy for glaucoma.²⁶ Apneic spells ceased after discontinuation of timolol.²⁶ In the randomized trial that supported use of intraocular timolol maleate gel-forming solution (GFS) in children with glaucoma, 3 of 72 subjects (4%) developed bradycardia or hypotension.²⁷

Pharmacokinetics of topical application of timolol for IH: Information regarding the PK of topical timolol in children is limited. Studies in adults with intraocular application have indicated systemic absorption of up to 80% of each drop of 0.5% timolol solution.²⁸ In a limited PK study (5 pediatric subjects) of intraocular application of 0.5% timolol solution, plasma timolol concentrations ranged from 3.5 ng/mL in a 5-year-old to 34 ng/mL in a 3-week-old.²⁹ Although the GFS form of timolol is thought to have lower systemic absorption compared to the solution, the likelihood of transcutaneous absorption is potentially increased when timolol is applied to the highly vascularized or ulcerated tissue of IH, or in the presence of occlusion (e.g., diaper hemangiomas).¹² Moreover, compromised barrier function of preterm infant skin and smaller volume of distribution relative to adults may lead to increased systemic absorption when compared to adults.¹² Previous investigators measured plasma concentrations of timolol 30 minutes after applying timolol solution to occluded skin over IH after treatment with fractionated CO₂ laser.³⁰ Timolol concentrations were below the limit of detection (20 pg/mL) in all 9 infants. An additional small study demonstrated absorption in all patients sampled (average of 0.18 ng/dL), but the biologic significance of this is unknown.³¹

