2.3.1.2 Risks of topical timolol therapy

Transcutaneous absorption of topical timolol solution has not been extensively studied in adults or children. Application of topical timolol to highly vascularized or ulcerated tissue of infantile hemangiomas or under occlusion (e.g. diaper hemangiomas) may increase transcutaneous absorption, and pose a greater risk of adverse events associated with systemic beta-blockers. Effects of systemic beta blockade include bronchial hyperreactivity, hypotension, bradycardia, hypoglycemia, sleep disturbance, hypothermia, and changes in extremity color or temperature e.g., coldness. Infants with known baseline risk factors for bradycardia, hypoglycemia, or bronchial hyperreactivity will be excluded from enrollment according to the protocol's predefined

criteria. More specific to the topical application of timolol, irritation or dermatitis may occur.

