6 STUDY PROCEDURES

6.1 Summary of Procedures

Table 6-1: Schedule of Study Procedures

Time (Day)*	Screen/ Baseline	Treatment phase							
	0 ¹ Visit #00/ Visit #01 ⁸	30 (±5 days) Visit #02	60 (± 5 days) Visit #03	90 (± 5 days) Phone contact Visit #04	120 (± 5 days) Visit #05	150 (± 5 days) Phone contact Visit #06	180 (± 5 days) Visit #07	Day 7 (+ 5 days) Phone contact post 180 day study period or early withdrawal Visit #08	Day 270 (± 5 days) Phone contact Confirm ongoing therapy Visit #09
Informed consent	X								
Demographics	X								
Randomization	X								
Vitals: HR, BP ¹⁰	X ⁸	X	X		X		X		
Physical Exam of lesion ²	X	X	X		X		X		
Photograph of lesion	X	X	X		X		X		
Medical History	X								
Physical Exam (systems assessment) ⁹	X	X	X		X		X		
Actual Weight	X	X	X		X		X		
Study Drug Dispensation	X	X	X		X				
Review of Participant Diary (Treatment Administration Info)	X	X	X		X		X		
SOC Timolol Dosing Info (from Phone Script/Follow-up Diary)								X	X
Concomitant Medications	X	X	X	X	X	X	X	X	
Adverse Events	X ^{4,8}	X	X	X	X	X	X	X	X ³
Blood sampling ⁵	X	X	X		X		X		
Parent reported QOL Survey ⁷	X		X				X		
Hemangioma Dynamic Complication Scale ⁶	X	X	X		X		X		
Assessment for treatment failure		X	X		X		X		

¹ Refers to time point prior to start of study drug and may be the same calendar date as day 1.

² This includes treating physician's assessment by Visual Analog Scale (VAS) and measure of width and

thickness. Note: VAS should only be performed at visits 02, 03, 05, 07 and unmasking.

³AEs of special interest will include bradycardia, hypotension, new alteration in mental status, new local skin irritation, new sleep disturbance, apnea, bronchospasm, hypoglycemia, and diarrhea.

⁴AEs will be collected following initial study-specific procedure (e.g., screening, blood draws, dosing)

⁵For infants who are enrolled into the PK portion of the study; up to 3 samples will be obtained throughout the study period and at least one sample should be collected within 2 hours of dosing. Clinic visits for infants in the PK portion of the study will be scheduled to fall within the appropriate time period. Blood pressure and heart rate must be collected within 15 minutes before or after sample collection.

⁶The Hemangioma Dynamic Complication Scale must be collected for all participants.

⁷The parent-reported QOL survey is not required for non-English speaking parents.

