8.1.4 Identification of Events and Timeframe for Reporting

Pre-existing conditions will not be considered as adverse events. New events that occur or pre-existing conditions that worsen in terms of frequency or intensity will be reported as adverse events.

All reportable events as defined above, determined to be an AE based on physical examination, laboratory findings, or other means, will be reported in the electronic case report form (e-CRF). The investigator will provide the date of onset and resolution, intensity, action(s) taken, changes in study drug dosing, relationship to study drug, and outcome.

Any event excluding adverse events of special interest beginning more than 7 days after the last dose of study drug or last study procedure will not be reported. For participants in the treatment arm adverse events of special interest only will be reviewed and reported at 90 days after the last dose of study drug.

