4. Absolute change in hemangioma dynamic complication scale from Day 0 to end of study within each treatment arm.
5. Assess time to partial response by comparing baseline to day 30, day 60, day 120 and day 180 in both treatment arms.
6. Absolute change in IH-QoL score scale from Day 0 to end of study within each treatment arm.

Secondary **safety** endpoints are the rate of serious adverse events and adverse events of special interest (Section 8.1.2) from randomization to Day 180 in infants treated with topical timolol maleate (0.25% and 0.5%) GFS for the treatment of infantile hemangioma.

Exploratory Endpoints:

Exploratory PK endpoints include estimation of PK parameters such as clearance (CL), volume of distribution (V), area under the curve (AUC), and maximum concentration (C_{max}), as possible.

The relationship between different hemangioma characteristics and plasma concentrations may also be described as an exploratory endpoint.

Treatment Failure for Partial Response in Hemangioma Color or Volume

The infant will be considered a treatment failure for the primary endpoint of partial response of VAS-volume or the secondary endpoint of partial response of VAS-color from baseline to Day 180 if any of the following conditions are met:

1. Partial response not achieved at the Day 180 visit in infants who complete the 180-day treatment period.
2. Infant withdrawn from masked treatment due to progressive disease. This will include participants randomized to the 0.25% treatment arm and switched to the 0.5% treatment arm.
3. Ulceration of the target hemangioma after initiation of masked treatment.
4. Infant withdrawn from study treatment due to safety concerns.
5. Study drop-out or loss to follow-up after the 30-day visit and before the 180-day visit for reasons other than progressive disease, ulceration, or safety concerns without having achieved partial response at the last study visit before drop-out.

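### The list of adverse events of special interest leaves out hypothermia and extremity colour or temperature change, which the protocol itself attributes to systemic beta blockade

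*Combined protocol and SAP*

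**What the plan says.** Section 2.3.1.2 sets out what systemic beta blockade may do to these infants. Its list starts with bronchial hyperreactivity, hypotension and bradycardia and ends with "hypoglycemia, sleep disturbance, hypothermia, and changes in extremity color or temperature e.g., coldness". Section 2.1 also describes an infant on ophthalmic timolol and other glaucoma drugs: "the infant developed altered mental status, hypotonia, hypothermia, bradycardia, apnea, hypotension", among other signs.

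Section 8.1.2 then states that "we will specifically evaluate infants for the following adverse events of special interest" and lists ten items: bradycardia, hypotension, altered mental status, local skin irritation, sleep disturbance, apnea, bronchospasm, hypoglycemia, diarrhea and arrhythmias. Table 6-1 footnote 3 repeats the list without arrhythmias, ending with "new sleep disturbance, apnea, bronchospasm, hypoglycemia, and diarrhea".

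Two other sections depend on that list. Section 10.1 defines the secondary safety endpoint as "the rate of serious adverse events and adverse events of special interest (Section 8.1.2) from randomization to Day 180". Section 8.1.4 sets the reporting cut-off: "Any event excluding adverse events of special interest beginning more than 7 days after the last dose of study drug", or after the last study procedure, goes unreported. From there to 90 days after the last dose, only events of special interest are reviewed.

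**The concern.** The list decides three things: what is asked about by name, what enters the secondary safety endpoint, and what is still reported once the 7-day period is over. Two effects that the protocol ascribes to the drug class fail all three, and no reason is given.

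This matters because Section 2.1 faults earlier topical timolol studies for scant prospective safety monitoring, and Sections 2.1 and 2.3.1.2 warn that absorption may rise on vascular, ulcerated or occluded lesions and through preterm skin. Cold or discoloured hands and feet are something a parent can notice at home. Nothing else in the schedule would reliably pick up either effect. Table 6-1 schedules heart rate and blood pressure but no temperature, and the systems examination is done only where it is local standard of care.

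**Working it through.** **Step 1. Compare the two lists.**

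| Effect named in 2.3.1.2 | In 8.1.2? | In Table 6-1 footnote 3? |
|---|---|---|
| Bronchial hyperreactivity | Yes, as bronchospasm | Yes |
| Hypotension | Yes | Yes |
| Bradycardia | Yes | Yes |
| Hypoglycemia | Yes | Yes |
| Sleep disturbance | Yes | Yes |
| Hypothermia | No | No |
| Extremity colour or temperature change | No | No |

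Five of seven are covered and two are absent. Section 8.1.2 has ten items and the footnote nine; the difference is arrhythmias.

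**Step 2. Follow an isolated, non-serious case through the plan.**

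- *On treatment and to 7 (+5) days after:* it is collected as an ordinary adverse event. Table 6-1 marks adverse events at every contact, Section 8.1.9 has staff solicit them, and Section 10.4.6 tabulates all of them by system organ class and preferred term. Nobody is told to ask about it by name.
- *Secondary safety endpoint (10.1):* it is neither serious nor on the 8.1.2 list, so it does not count.
- *Onset after the 7-day cut-off (8.1.4):* it is not reported. The 90-day contact takes place, asks about the listed events and, in Table 6-1, records standard-of-care timolol dosing and whether therapy is ongoing. Some infants may therefore still be exposed then.

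The endpoint stops at Day 180, so for infants who complete treatment the last gap is separate from the endpoint.

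**Step 3. Reproduce the figures in Section 10.3.** Inputs from that section: n = 100, rates of 20% (events of special interest) and 5% (serious), 95% Wilson intervals.

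Wilson interval: [p + z²/(2n) ± z·√(p(1−p)/n + z²/(4n²))] / (1 + z²/n), with z = 1.96 and z² = 3.8416.

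- p = 0.20: centre 0.219208/1.038416 = 0.2111; half-width 1.96 × √(0.0016 + 0.00009604)/1.038416 = 0.0777. Interval (0.133, 0.289), width 0.155. Plan: (0.13, 0.29), 0.16.
- p = 0.05: centre 0.069208/1.038416 = 0.0666; half-width 1.96 × √(0.000475 + 0.00009604)/1.038416 = 0.0451. Interval (0.022, 0.112), width 0.090. Plan: (0.02, 0.11), 0.09.
- Chance of at least one event: 1 − 0.99¹⁰⁰ = 0.634 and 1 − 0.95¹⁰⁰ = 0.994. Plan: 0.63 and 0.99.

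All agree after rounding.

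**Step 4. Bound the undercount.** The documents give no rate for the two effects. Assume, for illustration only, that 1% to 5% of 100 infants have one of them, all non-serious: 100 × 0.01 = 1 to 100 × 0.05 = 5 infants. Those who also have a listed event are already counted. The number missing is therefore 0 if overlap is complete and 1 to 5 if there is none.

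**Step 5. Effect of adding the terms on precision.** If the rate rose from 20% to the values below (assumption), the same formula gives:

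| Rate | 95% Wilson interval | Width |
|---|---|---|
| 20% | (0.13, 0.29) | 0.155 |
| 21% | (0.14, 0.30) | 0.158 |
| 22% | (0.15, 0.31) | 0.161 |
| 25% | (0.18, 0.34) | 0.168 |

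Precision hardly changes.

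**The case against.** The best reply is that Section 2.3.1.2 describes general class effects and nothing obliges the list in 8.1.2 to reproduce them. The list covers cardiac, respiratory, metabolic and central nervous effects, and adds apnea, arrhythmias and mental status. The secondary objective is only to describe safety, which the full adverse event tables serve. The two extra terms are also nonspecific when reported by parents. This stands as a reason to call the matter an improvement, not an error. It does not explain the omission: the list already accepts parent-reported diarrhea and sleep disturbance, which are no more specific, and diarrhea is not among the effects in 2.3.1.2.

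A reader might infer more than the documents support in five ways.

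- *That these events are lost during treatment.* They are not. They are collected and tabulated; what is missing is targeted questioning, entry into the endpoint and later follow-up. The diary and phone scripts are not in the documents and may already ask.
- *That the detection probabilities in 10.3 fail for these effects.* The 0.63 and 0.99 refer to events seen in the study population, so they stand. A zero chance within the endpoint is true by definition of any unlisted term.
- *That a fixed number of infants is missing.* This ignores overlap. The infant in Section 2.1 with hypothermia also had altered mental status, bradycardia, apnea and hypotension, all listed, and would have been counted.
- *That a systemic-effect rate is understated.* The plan has no such endpoint; its rate also includes local skin irritation and diarrhea.
- *That parents can see both effects unaided.* This fits extremity change. Low temperature generally needs a thermometer.

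**Conclusion.** The point holds as a gap in targeted safety ascertainment. Two effects that the protocol attributes to systemic beta blockade are on neither list. An isolated non-serious case is therefore not specifically solicited, does not count in the secondary safety endpoint, and is not reported if it starts after the 7-day cut-off. Until then it still appears in the general adverse event tables.

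The size is unknown. Under the assumed 1% to 5%, it is at most 1 to 5 infants per 100, and fewer with any overlap. No analysis is invalidated and no figure in Section 10.3 needs correcting. The change is worth making because it is cheap and no scheduled measurement would otherwise find these effects. The mismatch over arrhythmias between 8.1.2 and the footnote is a separate inconsistency that needs reconciling in any case.

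**What to change.** - Add hypothermia and new change in extremity colour or temperature to Section 8.1.2 and to Table 6-1 footnote 3. The sponsor sets the case definition and the accepted source of report, as it did for most of the listed terms.
- Reconcile the two lists on arrhythmias.
- Ask about both terms at the existing visits and calls, including the Day 7 post-treatment and Day 270 calls; check the diary and phone scripts and add the prompts if they are not there.
- Count both terms in the Section 10.1 safety endpoint, and have Section 10.4.6 report each term of special interest separately beside the overall proportion.

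The cost is two lines of text in each list and two questions at contacts that already take place. The downside is that nonspecific parent reports may raise the crude rate slightly; reporting by term lets a reader see where a rise comes from.

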8.1.3 Unexpected Adverse Event

This is defined as any adverse event, the specificity or severity of which is not consistent with the package insert or investigational plan.

8.1.4 Identification of Events and Timeframe for Reporting

Pre-existing conditions will not be considered as adverse events. New events that occur or pre-existing conditions that worsen in terms of frequency or intensity will be reported as adverse events.

All reportable events as defined above, determined to be an AE based on physical examination, laboratory findings, or other means, will be reported in the electronic case report form (e-CRF). The investigator will provide the date of onset and resolution, intensity, action(s) taken, changes in study drug dosing, relationship to study drug, and outcome.

Any event excluding adverse events of special interest beginning more than 7 days after the last dose of study drug or last study procedure will not be reported. For participants in the treatment arm adverse events of special interest only will be reviewed and reported at 90 days after the last dose of study drug.

8.1.5 Follow-up of Adverse Events

All events (study-related or not) must be followed to adequately evaluate the infant's safety or until the event stabilizes/resolves. Any safety event that is identified at the last assessment (or an early termination) must be recorded on the appropriate eCRF with the status of the safety event noted. All serious suspected adverse reactions and serious adverse reactions will be followed until resolution or until the infant is medically stable. All other events that cannot be resolved by 37 days after the last study dose or last study procedure, as applicable, will have the status of the ongoing event entered in the electronic data capture (EDC) system at that time.

8.1.6 Guidelines for Assessing Grade of an Adverse Event

The investigator should use the following definitions when assessing intensity of an adverse event:

1. **MILD:** Participant is aware of symptoms or has minor findings but tolerates them well, and no or minimal intervention required.
2. **MODERATE:** Participant experiences enough symptoms or findings to require

intervention.

3. **SEVERE:** Participant experiences symptoms or findings that require significant intervention.

8.1.7 Guidelines for Determining Causality

The investigator will use the following question when assessing causality of an adverse event to study drug, where an affirmative answer designates the event as a suspected adverse reaction: Is there a reasonable possibility that the drug caused the event? “Reasonable possibility” means that there is evidence to suggest a causal relationship between the drug and the adverse event.

8.1.8 Discontinuation of a Participant Due to Adverse Events

Infants may be withdrawn from the study at any time. Infants withdrawn from the study due to an AE, whether serious or non-serious, must be followed by the investigator until the clinical outcome from the AE is determined. Any infant who experiences an AE may be withdrawn at any time from the study at the discretion of the investigator. The AE(s) should be noted on the appropriate CRFs, and the infant’s progress should be followed until the AE is resolved or considered stable. The Medical Monitor and the Protocol Chair/PI must be notified.

8.1.9 Reporting Procedures

Information about AEs will be solicited by investigators and study coordinators.

All adverse events will be entered into the safety data system within 7 days of study staff identification. Serious events will be entered into the data system within 24 hours of study staff identification. If there are any technical difficulties, the SAE will be reported by direct communication with the Medical Monitor.

8.2 Serious Adverse Events

Any serious adverse event entered in the safety database will generate an automatic email notification to the DCC, IND sponsor and funding sponsor. The DCC medical monitor will review all SAEs at the time that they are reported but no later than one business day. Investigators must also submit safety reports locally as required by their IRB.

8.3 Regulatory Reporting

Any event that requires expedited reporting based on federal regulations will be forwarded to the IND sponsor. The IND sponsor will submit expedited safety reports (e.g. IND safety reports) to the regulatory agencies as necessary, and will inform the investigators of such regulatory reports. Site investigators must submit safety reports as required by their IRB. Documentation of the submission and receipt by the IRB must be retained for each expedited safety report.

All serious events irrespective of their designation as “related” or “not related” to study product(s) will be reported to the FDA at least annually in a summary format.

8.4 Safety Oversight

The DMC will review serious adverse events at regularly scheduled meetings. In addition, a qualified and experienced clinician not otherwise associated with this protocol will serve as the medical monitor. The medical monitor will review all SAEs at the time they are reported. If safety concerns are identified, the medical monitor may request a meeting of the DMC to review safety data. At a minimum, the medical monitor will comment on the outcomes of the SAE and causal relationship of the SAE to the study product. The medical monitor will also indicate whether he/she concurs with the details of the report provided by the study investigator. If no SAEs prompt review at an earlier time point, the DMC will review AEs and SAEs at the regularly scheduled meeting. The DMC will convene and make recommendations on termination of the study based on review

of safety reports and halting rules. The safety data will be compiled by DCC. Based on the recommendations of the DMC, NIH and IND sponsor will make a decision to terminate or continue the study.

